4.1 IVPCA

4.1.1 - Immediately following surgery, the OR Anesthesia team will titrate intravenous narcotics in the PACU for pain down to an acceptable level prior to initiating IVPCA. All patients assigned to IVPCA group will be started on intravenous patient-controlled analgesia protocol according to current institutional policy following surgical procedures. All patients will be given hydromorphone as the opioid of choice per current practice, unless there are contraindications. Fentanyl or Morphine will be secondary alternatives. Initial recommended starting doses are: no basal rate, 0.2mg every 10 minutes demand dosing, and a 0.5mg nursing bolus every 1 hour as needed for additional pain control (Appendix A). Adjunctive use oral, rectal, or intravenous non-narcotic analgesics (acetaminophen, non-steroidals, etc.) will be utilized at the discretion of the Primary Surgical Team.

4.1.2 - Patients whose IVPCA's are not functioning or not providing adequate analgesia will be considered for possible postoperative placement of TEA (coagulation studies permitting) as an alternative analgesic regimen (patient crossover).

4.1.3 - Further drug information can be found in the MDACC formulary and the FDA approved package inserts of the medications as they are all commercially available.

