6.5 Postoperative Pain Assessment (Both TEA and IVPCA Groups)

6.5.1 - Pain scores will be assessed in both groups with a Numeric/Visual Pain Scale (0-10) at various time points in the clinical record per current inpatient policies (Appendix F). Beginning in the PACU after surgery, pain will be assessed by nursing staff approximately every hour per current practice until disposition to inpatient care units. In the overnight recovery suite and general floor pain will be assessed by nursing staff approximately every 4 hours per current practice. In the SICU pain will be assessed by nursing staff approximately every hour per current practice. The pain assessments that are being used for analysis are average pain scores within first 6hrs postop, the next 18hrs, and each 24hr period thereafter. The pain scores for each 24 hour period after this will be averaged (as many as are collected). Pain will re-assessed by nursing staff approximately 1 hour after every analgesic intervention per current practice on all nursing floors. All dosing alterations, changes, and total narcotic/analgesic use will be documented in the clinical record per current practice.

6.5.2 - The Acute Pain Service team/nurse will assess all patients in both groups (TEA and IVPKA). Therapeutic analgesic interventions in the TEA group will be per discretion of the Acute Pain Service per current practice. Therapeutic interventions in the IVPKA group will be per discretion of the primary surgical team per current practice and the primary surgical team will be blinded to the Acute Pain Service assessment of patients in IVPKA group.

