7.1 Primary Endpoints

7.1.1 - Pain scores (Numeric/Visual Pain Scale)

Pain score AUC within the first 48 hours will be used as the primary endpoint. The AUC for each patient will be computed using the trapezoidal method using the pain score versus time curve. The mean AUC pain scores within the first 48 hours will be compared between TEA and IVPKA groups for the primary analysis.

7.1.2 - Quality of Life

- Patients will complete a validated SF-8, Acute Recall QOL survey (preoperatively and then at approximately 24hrs after surgery) (Appendix G)
- Patients will complete a validated SF-36v2, Acute Recall QOL survey (preoperatively and then prior to discharge or at approximately 1 week after surgery – whichever is first) (Appendix H).

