endpoint for pain scores is mean pain scores within the first 48 hours, computed as the AUC the pain score vs. time curve for each individual. In case there is missing data, we will compute the AUC while using last value carried forward to fill in the missing data. For primary analysis, 2-sample t-tests or Wilcoxon rank sum test will be used to compare mean pain scores within 48 hours post operation between TEA and IVPCA arms. The same methods will also be applied to compare mean pain scores at each time point between TEA and IVPCA. Linear mixed models including treatment, evaluation time, and interaction of treatment and evaluation time will be fit to determine the treatment effect on pain scale. Each pain score in PPS form will be analyzed for the primary analysis. Chi-square test or Fisher's exact test will be used to compare the binary outcomes between the two arms, which are related to effects of pain on patients' movement or mood, such as pain's influence on mobility or movement, cough or breath deeply, sleep and mood. Generalized estimating equation (GEE) regression models will be fit to estimate the treatment effects on the listed binary outcomes. Chi-square test will be used to compare the categorical items of QOL pre and post surgery between the two treatment arms, the same method will also be used to compare the changes pre-postoperative in items of QOL between the two arms as well.

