8.2 Sample Size

- A total of 200 liver and pancreatic resection patients will be enrolled in order to achieve 140 evaluable patients. As these surgical procedures are for resection of malignancy, a proportion of patients will be identified with unresectable or metastatic disease at the time of planned resection either during initial laparoscopy or after open exploration. Those patients deemed unresectable at laparoscopy will not undergo open exploration, and thus, will be inevaluable for postoperative pain due to differences in incision type. Furthermore those patients that do undergo an open exploration but are deemed unresectable due to local or metastatic disease found intraoperatively will have markedly different prognoses compared to those that have a successful resection, which may bias their response to pain and quality of recovery and bias the questionnaire responses. Based on previous work at our and other institutions, it is expected that up to 30% of patients will not be evaluable due to various reasons, including ineligibility, patient withdrawal from the study, unresectable disease, and failure to complete or inaccurate completion of questionnaires. Based on historical information, if the difference in mean pain score between the two evaluable treatment groups of patients is 1 and the common standard deviation is 1.5, with a total of 140 evaluable patients (105 in TEA group and 35 in IVPCA group), the study will yield a 92% power to detect the difference, using a two-sample t-test at a two-sided significance level of 0.05. Furthermore, the study will have a 99% power to detect a difference of 10 in QOL score with a corresponding standard deviation of 9 using a two-sided Student's t-test with a type I error of 0.05. All statistical analyses will be performed with an intent to

treat methodology, including those patients who cross over between treatment groups.

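### Last value carried forward is a poorer rule for gaps in the primary 48-hour pain AUC than the trapezoid plus a model for missing ends; the effect is probably small and its direction unknown

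*Combined protocol and SAP*

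**What the plan says.** Section 7.1.1 defines the primary endpoint: "Pain score AUC within the first 48 hours will be used as the primary endpoint". It also gives the method: "The AUC for each patient will be computed using the trapezoidal method using the pain score versus time curve". Section 8.1 describes the same quantity as the mean pain score over 48 hours and adds the missing-data rule: "In case there is missing data, we will compute the AUC while using last value carried forward to fill in the missing data". The rule draws no line between gaps with a score on both sides, gaps at the end and a missing first score. No sensitivity analysis is attached to it.

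The primary comparison follows in section 8.1: "2-sample t-tests or Wilcoxon rank sum test will be used to compare mean pain scores within 48 hours post operation". The section also plans a repeated-measures analysis, "Linear mixed models including treatment, evaluation time, and interaction of treatment and evaluation time will be fit", but does not link it to missing scores.

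Scoring times are approximate. Section 6.5.1 plans roughly hourly scores in the PACU and SICU. Elsewhere, "In the overnight recovery suite and general floor pain will be assessed by nursing staff approximately every 4 hours per current practice". For the period averages, the same section uses whatever scores exist and fills nothing.

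**The concern.** The trapezoid at actual times needs no filled value inside a gap, because it joins the scores on either side. Inserting a carried value discards the information in the later score. At the end of the record there is no later score, and carrying forward assumes that pain stays where it was last seen. In both cases the filled value enters the test as if it had been observed.

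The rule acts directly on the primary endpoint. If the arms differ in how pain changes over time, or in how often and how long scores are missing, part of the bias passes into the treatment contrast. The trial is not blinded and its charting times are approximate, so the rule should leave little discretion over where values are filled.

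**Working it through.** **Inputs from the documents.** The window is 48 h (section 7.1.1). Scores come about every 4 h on the floor and in the overnight suite (6.5.1). Section 8.2 gives a difference of 1, SD 1.5, 105 and 35 evaluable patients, two-sided 0.05 and power 92%.

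**Assumptions.** The documents give no pain trajectory, so the curves are mine: a linear fall from 6 to 3 or 5 to 3 over 48 h; an exponential fall 3 + 3·exp(−t/12); a flat curve; a linear rise from 3 to 5; and a rise and fall 2 + 3·exp(−((t − 18)/9)²). Scores lie on a 4-hourly grid from 0 to 48 h. The 48-hour mean is AUC/48.

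**1. The plan's power.** SE = 1.5 × √(1/105 + 1/35) = 0.293, and 1/0.293 = 3.42. The noncentral t distribution with 138 degrees of freedom gives 92.4%, which reproduces the stated 92%.

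**2. Interior gaps.** On the linear fall from 6 to 3, pain drops 0.25 per 4 h. Successive carried values are too high by 0.25, 0.50 and 0.75, and each has weight 4/48:
- one reading: 0.25 × 4/48 = 0.021
- two readings: 0.75 × 4/48 = 0.0625
- three readings: 1.50 × 4/48 = 0.125

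Error in the 48-hour mean:

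| Missing readings | Linear, carried | Linear, joined | Exponential, carried | Exponential, joined |
|---|---|---|---|---|
| 8 h | +0.021 | 0.000 | +0.051 | +0.007 |
| 8, 12 h | +0.0625 | 0.000 | +0.138 | +0.025 |
| 16, 20, 24 h | +0.125 | 0.000 | +0.129 | +0.027 |

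A steeper case is a score of 7, one carried reading, then 3 at 8 h. Carried: 7×4 + (7+3)/2×4 = 48 point-hours. Joined: (7+3)/2×8 = 40. The excess is 8/48 = 0.17 points on the 48-hour mean.

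**3. Trailing gaps.** For a linear fall of slope b with last score at time s, the excess is b × (48 − s)²/(2 × 48).
- 6 to 3 (b = 3/48): s = 24 gives 0.0625 × 576/96 = 0.375; s = 12 gives 0.0625 × 1296/96 = 0.84.
- 5 to 3 (b = 2/48): 0.25 and 0.56.
- Exponential fall, s = 24: 0.11.

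Dividing the truncated AUC by the observed time is worse. With the last score at 24 h, the error is +0.75 (linear, 6 to 3) or +0.57 (exponential). Trailing gaps therefore need their own rule.

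**4. Other shapes.** On the flat curve the carry-forward error is zero. On the rise from 3 to 5 it is −0.01 to −0.08 for the same interior gaps and −0.25 when scores end at 24 h. Joining is not better in every case: on the rise-and-fall curve, with 16 to 24 h missing across the peak, carrying gives −0.155 and joining −0.287.

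**5. The contrast.** The shift in an arm mean is the share affected times the per-patient error. With 10% affected in one arm and none in the other, it runs from 0.10 × 0.25 = 0.025 to 0.10 × 0.84 = 0.084, at most 0.084/0.293 = 0.29 standard errors. If 0.08 came wholly off the planned difference, power would be about 88%. A net difference in bias of 0.1 would give 86% if it shrinks the difference and 96% if it inflates it.

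**The case against.** The strongest reply is that little is at stake. Planned charting is hourly or 4-hourly, so long gaps should be uncommon, and section 5 above puts the arm-level shift at a fraction of a standard error. The mixed model and the unfilled period means (sections 6.5.1 and 7.2.4) already cover the same 48 hours. The carry-forward sentence could also be meant only for records that stop early.

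The point about size stands. The other two do not settle the matter. The mixed model and period means are not tied to the primary AUC, so its stated rule still governs the primary test. The sentence also makes no exception for interior gaps.

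A reader might infer more than the documents support:
- *That carry-forward overstates pain.* This holds only on a falling curve. For the IVPCA arm, section 4.1.1 says the anesthesia team "will titrate intravenous narcotics in the PACU for pain down to an acceptable level prior to initiating IVPCA". That suggests an early fall in that arm, and pain may be flat afterwards.
- *That the rule favours one arm.* Section 2.2 links systemic opioids to sedation, section 2.7 cites a pancreatic series with more intensive care admissions under epidural analgesia, and both arms receive hydromorphone. No missingness rates are given.
- *That the carried score is often a high one that prompted treatment.* Section 6.5.1 plans a new score about an hour after each analgesic intervention.
- *That withdrawn patients drive the problem.* Section 8.2 counts withdrawal among the reasons for being non-evaluable, although it also states an intent-to-treat approach.
- *That an interior gap can cost a full point.* In the 7-to-3 example the means are 6.0 and 5.0 over the 8-hour segment only; over 48 hours the difference is 0.17.

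**Conclusion.** The concern holds as a matter of method, with a modest expected effect. For interior gaps, carrying forward is generally inferior to the trapezoid the plan already specifies, except where a gap hides a peak. For trailing gaps it rests on an untested assumption of constant pain. Errors for a single patient can be sizeable when scores stop early, up to 0.84 points on the assumed linear fall. An arm mean moves by only about 0.03 to 0.08 points if a tenth of that arm is affected, against a planned difference of 1 and SD of 1.5.

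These sizes depend on assumed curves and an assumed share of patients. The contrast is biased only if trajectory or missingness differs between arms, and the documents do not establish the direction. The stated power reproduces, and the sample size is unaffected. The change is worth making because it is cheap and concerns the primary endpoint.

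**What to change.** Replace the carry-forward sentence in section 8.1 with a rule of this kind:

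- Compute the AUC by the trapezoid on observed scores at their actual times, and fill no interior gap.
- When scores end before 48 h, or the first score is missing, use multiple imputation with arm, resection stratum and the patient's observed scores. Pool the difference in 48-hour means across imputations as the primary result. State how close to 0 and 48 h the first and last scores must lie for a record to count as complete.
- Report two sensitivity analyses: the 48-hour time-averaged difference from the linear mixed model already planned, and the AUC with last value carried forward.

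Reporting the number and length of interior and trailing gaps by arm would show whether the choice mattered. The cost is revised wording and slightly more programming. Data collection, sample size and trial conduct do not change.

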3.0 Patient Eligibility

3.1 Inclusion Criteria:

3.1.1 - Patients undergoing liver and/or pancreatic surgical resection for malignancy at MD Anderson Cancer Center.

3.1.2 - Patients 18 years of age and older. There will be no upper age restriction.

3.1.3 - Patients must sign a study-specific consent form.

3.1.4 - Adequate coagulation function within 30 days of surgery:

- Platelets $\geq 100,000/\text{ml}$
- INR ≤ 1.5
- aPTT ≤ 40

3.1.5 - Patients must have no fever or evidence of infection or other coexisting medical condition that would preclude epidural placement.

3.2 Exclusion criteria:

3.2.1 - Evidence of severe uncontrolled systemic disease or other comorbidity that precludes liver or pancreatic surgery.

3.2.2 - History of chronic pain, long-term narcotic use or being considered for chronic pain consultation postoperatively.

3.2.3 - Anaphylaxis to local anesthetics or narcotics.

3.2.4 - Previous or current neurologic disease affecting the lower hemithorax or below.

3.2.5 - Major open abdominal/thoracic surgery in the previous 30 days under general anesthesia, except for TIVA (total intravenous anesthesia).

3.2.6 - Technical contraindications to epidural placement: previous thoracic spinal surgery or local skin or soft tissue infection at proposed site for epidural insertion.

3.2.7 - Ongoing use or planned peri-operative use of anticoagulants (not including DVT prophylaxis).

3.2.8 - Known bleeding diathesis or coagulopathy.

3.2.9 - Educational, psychiatric (untreated or poorly controlled schizophrenia, major depression, or bipolar disorder), or communication (language) barrier that would preclude accurate assessment of postoperative pain and/or ability to answer questionnaires (need to be able to read, comprehend, and answer questions).

3.2.10 - Inability to comply with study and/or follow-up procedures.

3.2.11 - Patient refusal to participate in randomization.

3.2.12 - Pregnant women are excluded from this study; women of childbearing potential (defined as those who have not undergone a hysterectomy or who have not been postmenopausal for at least 12

consecutive months) must agree to practice adequate contraception and to refrain from breast-feeding, as specified in the informed consent.

3.2.13 - Patients with obvious unresectable disease prior to signing informed consent.

4. Treatment Plan - Analgesic Regimens

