4.2 TEA

4.2.1 - All patients assigned to TEA will have thoracic epidurals placed preoperatively in either the holding area or in the operating room according to current institutional protocol. Epidural catheters will be placed between the Thoracic 5th-Thoracic 10th interspinous levels using standard technique according to institutional practices. All epidural catheters will be tested for correct placement and level of block documented and secured as is currently practiced. The epidural will be initially dosed according to current practices with hydromorphone (10 mcg/kg for pts 65 yrs or younger and 5 mcg/kg for pts > 65yrs) after induction of anesthesia. Standard epidural solutions are: Hydromorphone (10 mcg/ml for pts 65yrs or younger and 5 mcg/ml for pts > 65yrs) and Bupivacaine (0.075%) at 10 ml/hr continuous infusion and a 3ml every 10 minutes demand dosing, and a 5ml every 3 hours clinician bolus as needed for additional pain control (Appendix B). Fentanyl with Bupivacaine

will be secondary alternatives. Adjunctive use of oral, rectal, or intravenous non-narcotic analgesics (acetaminophen, non-steriodals, etc.) will be utilized at the discretion of Acute Pain Service and/or Primary Surgical Team. Epidural catheters will remain in place a maximum of 7 days postoperatively. Epidural catheters will be removed once patients are successfully tolerating a full diet or tube feeds and are transitioned to oral/enteral analgesics. Indwelling urinary catheters will be removed after TEA removal per current policy.

4.2.2 - Patients whose TEA's are not functioning or not providing adequate analgesia will be considered for IVPCA as an alternative analgesic regimen (patient crossover).

4.2.3 - Further drug information can be found in the MDACC formulary and the FDA approved package inserts of the medications as they are all commercially available.

5. Treatment Plan – Perioperative Monitoring

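### The primary 48-hour pain comparison leaves out preoperative scores and age that are already available: a modest, avoidable loss of precision in a valid analysis

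*Combined protocol and SAP*

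**What the plan says.** Section 7.1 sets the pain endpoint: "Pain score AUC within the first 48 hours will be used as the primary endpoint". Section 8.1 gives the test: "For primary analysis, 2-sample t-tests or Wilcoxon rank sum test will be used to compare mean pain scores within 48 hours post operation". The only model for pain is also in section 8.1: "Linear mixed models including treatment, evaluation time, and interaction of treatment and evaluation time will be fit to determine the treatment effect on pain scale". No covariate is named for either. Section 8.2 plans the same unadjusted tests in the major-hepatectomy subset.

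Baseline information exists. Section 7.1 has "Patients will complete a validated SF-8, Acute Recall QOL survey (preoperatively and then at approximately 24hrs after surgery" and "Patients will complete a validated SF-36v2, Acute Recall QOL survey (preoperatively and then prior to discharge or at approximately 1 week after surgery". Section 8.1 reduces both instruments to physical and mental summary scores, but uses the preoperative values only for the quality-of-life comparisons. Age is an eligibility item in section 3.1 ("Patients 18 years of age and older. There will be no upper age restriction"), and section 4.2 sets the initial epidural dose by age: "hydromorphone (10 mcg/kg for pts 65 yrs or younger and 5 mcg/kg for pts > 65yrs".

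The trial is non-blinded and randomises 3:1, stratified by resection type only (section 8.1).

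**The concern.** If preoperative health status and age predict postoperative pain, a comparison that ignores them carries that variation as noise. Precision is limited by the smaller arm, with 35 planned evaluable IVPCA patients, and nothing in the design balances age or preoperative health between arms. Values already in hand could shrink the standard error without another patient or form.

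Prespecification also matters. In a non-blinded trial, an adjustment chosen after an imbalance has been seen is open to criticism; one written down beforehand is not.

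**Working it through.** **Inputs.** From section 8.2: difference 1 point, common SD 1.5, 105 TEA and 35 IVPCA evaluable patients, two-sided 0.05, stated power 92%. Assumed: r, the (multiple) correlation of the baseline covariates with 48-hour pain, from 0.1 to 0.5, since the documents give no value.

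**1. The plan's figure.** SE = 1.5 × √(1/105 + 1/35) = 1.5 × 0.195 = 0.293. Noncentrality is 1/0.293 = 3.42. Power from the noncentral t with 138 degrees of freedom is 92.4% (normal approximation 92.7%). The stated 92% reproduces.

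**2. With adjustment, same slope in both arms.** Residual SD = 1.5 × √(1 − r²). The equivalent number of extra evaluable patients at 3:1 is 140/(1 − r²) − 140. Power below allows for 1 degree of freedom lost; losing 3 changes it by about 0.0001.

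| r (assumed) | Residual SD | SE | Power at 1 point | Extra patients, equivalent |
|---|---|---|---|---|
| none | 1.50 | 0.293 | 92.4% | 0 |
| 0.1 | 1.49 | 0.291 | 92.6% | 1 |
| 0.2 | 1.47 | 0.287 | 93.3% | 6 |
| 0.3 | 1.43 | 0.279 | 94.5% | 14 |
| 0.4 | 1.37 | 0.268 | 95.9% | 27 |
| 0.5 | 1.30 | 0.254 | 97.5% | 47 |

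**3. Major-hepatectomy subset.** With 51 v 17 patients and the plan's effect of 0.796 SD, unadjusted power is 80.0%, as stated. Adjusted power is 81.5% (r = 0.2), 83.5% (r = 0.3) or 89.9% (r = 0.5).

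**4. Chance imbalance.** The between-arm difference in a standardised covariate has SD √(1/105 + 1/35) = 0.195, so the chance of exceeding 0.3 SD is 12%. At r = 0.4 an imbalance of 0.3 SD moves the pain difference by 0.3 × 0.4 × 1.5 = 0.18 points, which is 0.18/0.293 = 0.6 of one unadjusted standard error.

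**5. Unequal slopes at 3:1 (assumed case).** Suppose r = 0.4 in TEA and 0 in IVPCA, with SD 1.5 in both. The slopes are 0.4 × 1.5 = 0.6 and 0 points per covariate SD. A common-slope model fits about 0.75 × 0.6 = 0.45.

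- Residual variance, TEA: 2.25 − 2 × 0.45 × 0.6 + 0.45² = 1.9125. IVPCA: 2.25 + 0.45² = 2.4525.
- True SE: √(1.9125/105 + 2.4525/35) = 0.297, against 0.293 unadjusted.
- SE the model reports: pooled variance 0.75 × 1.9125 + 0.25 × 2.4525 = 2.0475, and √(2.0475 × (1/105 + 1/35)) = 0.279.

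Simulation agrees (0.299 true, 0.280 reported, 0.293 unadjusted). In this case the common-slope model is no more precise and its interval is too narrow.

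Adding a treatment-by-covariate term gives residual variances of 2.25 × 0.84 = 1.89 and 2.25. The true SE is then √(1.89/105 + 2.25/35 + 0.6²/140) = 0.291. The usual pooled-variance formula would report √((0.75 × 1.89 + 0.25 × 2.25) × (1/105 + 1/35)) = 0.275. So the extra term restores efficiency, but robust standard errors are what keep the interval honest.

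**The case against.** The case for leaving the plan alone is substantial.

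- **The test is valid.** A two-sample test in a randomised trial is unbiased, keeps its type I error and matches the sample-size basis in section 8.2. This stands in full.
- **Chance imbalance is not an added harm.** A reader might infer that, with 35 IVPCA patients, an imbalance in age or health would bias the pain result. The documents do not support that: such imbalance is equally likely in either direction and is already inside the standard error of 0.293 and the 92% power. The 0.18-point shift in step 4 is ordinary sampling error.
- **r may be low.** Section 3.2 excludes chronic pain and long-term narcotic use. Sections 4.1 and 6.5 describe analgesia being titrated to pain. The natural covariate, a preoperative 0–10 score, is not described; scoring starts after surgery ("Beginning in the PACU after surgery, pain will be assessed by nursing staff approximately every hour"). This also stands, and is why r = 0.1 is in the range.
- **The gain is not guaranteed at 3:1.** Section 4.2 splits the initial epidural dose at age 65, while the IVPCA starting dose in section 4.1 has no age split, so different age slopes by arm are plausible. Step 5 shows the consequence. This alters how the model should be specified; it does not remove the reason to adjust.
- **The preoperative forms may not be safe covariates.** Section 7.1 does not tie them to a time before randomisation, which section 8.1 also places before surgery. In a non-blinded trial, a form filled in after the arm is known could be affected by it. This stands and must be settled in the text.

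None of this defends leaving the values unused; it limits how much can be claimed.

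**Conclusion.** The point holds as a missed, low-cost gain in precision. No baseline value enters any planned pain analysis, although preoperative SF-8 and SF-36v2 scores are collected and age is available. That age is available is inferred from the eligibility and dosing rules; the plan does not list it as an analysis variable.

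Over an assumed r of 0.1 to 0.5, power at the design difference rises from 92.4% to between 92.6% and 97.5%. The gain is negligible at r of 0.2 or less (at most 0.9 percentage points, about 6 patients) and clear only from about r = 0.3. These figures assume equal covariate slopes in the two arms and the plan's SD of 1.5.

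A reader might go further and infer that the primary analysis is wrong or the trial underpowered. Neither follows: the stated 92% reproduces without adjustment, and nothing in the plan contradicts the use of a two-sample test.

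**What to change.** Prespecify as the primary analysis a linear model of the 48-hour pain endpoint on arm, with these terms and rules:

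- One named preoperative score, for example the SF-36v2 physical summary, from a form that the protocol requires to be completed before the allocation is known.
- Age, and resection type as the stratification factor.
- Covariates centred, with treatment-by-covariate terms or robust standard errors because of the 3:1 allocation. Robust standard errors are worth having even if the terms are included (step 5).
- Missing baseline scores filled with the overall mean across both arms.

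Report the adjusted difference with its 95% confidence interval. Keep the unadjusted t-test or Wilcoxon test as a sensitivity analysis. Carry the same covariates into the linear mixed model.

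The cost is a few sentences in section 8.1, one on form timing in section 7.1, and a few degrees of freedom. It needs no new visit, form or patient. If r is small, little is gained and little is lost.

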8.0 Statistical Considerations

8.1 Methodology

- This is a two-arm randomized non-blinded study whose primary objectives are to compare postoperative pain scores and quality of life (QOL) scores in patients undergoing liver and/or pancreatic resection between those receiving TEA versus IVPCA. Eligible patients will be randomized in a 3:1 allocation ratio to the treatment group of TEA or IVPCA group (to represent our current institutional practice as well as to allow a more accurate determination of overall TEA failures and complications). Randomization will be stratified by the resection type (liver or pancreatic - 1:1). The randomization will be conducted by the CORE prior to surgery and after consent and registration. Pain will be assessed using a numeric/visual pain score at various timepoints. The pain scores will be averaged for each patient and be compared between TEA and IVPCA groups at specific time points as follows: pain scores for the first 6 hours after surgery, pain scores for the next 18hrs after surgery, pain scores for each subsequent 24hr period after surgery until postoperative day #5 or epidural removed, whichever occurs first. QOL will be assessed pre- and postoperatively using SF-8 and SF-36v2. These validated instruments will score 8 domains that will be reduced to two summary measures scales, Physical Component Summary (PCS) and the Mental Health Component Summary (MCS). Scoring will be performed utilizing proprietary certified scoring software from the vendor. QOL scores will be calculated and compared between the two groups of patients.
- Categorical data will be tabulated with frequency and percentages, and continuous variables will be summarized using descriptive statistics mean, standard deviation, median and range. The primary

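### Randomisation is stratified by liver versus pancreatic resection, but the pain analyses leave the stratum out: a free, modest gain in precision

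*Combined protocol and SAP*

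**What the plan says.** Section 8.1 sets 3:1 allocation to TEA or IVPCA and names one stratification factor: "Randomization will be stratified by the resection type (liver or pancreatic - 1:1".

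The pain analyses then proceed without that factor:

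- Section 7.1: "The mean AUC pain scores within the first 48 hours will be compared between TEA and IVPKA groups for the primary analysis".
- Section 8.1, primary comparison: "2-sample t-tests or Wilcoxon rank sum test will be used to compare mean pain scores within 48 hours post operation".
- Section 8.1, individual time points: "The same methods will also be applied to compare mean pain scores at each time point between TEA and IVPCA".
- Section 8.1, longitudinal analysis: "Linear mixed models including treatment, evaluation time, and interaction of treatment and evaluation time will be fit". Resection type is not among the listed terms.
- Section 8.2, sample size: "the study will yield a 92% power to detect the difference, using a two-sample t-test".

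No other section adds resection type, or any other covariate, to a pain analysis.

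**The concern.** Stratified randomisation spreads liver and pancreas patients evenly over the arms, so most of any liver-pancreas difference in pain cancels out of the treatment contrast. A plain two-sample t-test does not use this. It puts the between-stratum variation into the pooled variance, and so reports a standard error larger than the true sampling error of the estimate.

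If resection type is related to pain, the confidence interval is wider than it need be, the test runs below its nominal 5% level, and some power is lost. If it is unrelated, adjustment costs one degree of freedom out of 138. The factor is already recorded at randomisation, so the improvement is essentially free. With only 35 evaluable IVPCA patients planned, precision is worth having.

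**Working it through.** **Inputs from section 8.2:** treatment difference 1 point, common SD 1.5, 105 TEA and 35 IVPCA evaluable patients, two-sided 5% level.

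**Assumptions:** the liver-pancreas difference in mean 48-hour pain, D, is not in the documents and is varied over 0, 0.5, 1.0 and 1.5 points. The total SD is held at 1.5. The 1:1 in the stratification sentence is read as roughly equal strata. Strata of 72 (54 TEA, 18 IVPCA) and 68 (51 TEA, 17 IVPCA) are used because both are then exactly 3:1 and sum to 105 and 35.

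**Step 1: the plan's own figure.** SE = 1.5 × √(1/105 + 1/35) = 1.5 × 0.1952 = 0.293. The noncentrality is 1/0.293 = 3.42 on 138 df, giving power of 92.4%. The stated 92% is right for the unadjusted t-test.

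**Step 2: remove the stratum variance.** With p = 72/140, the between-stratum variance is D² × p(1 − p) and the within-stratum variance is 2.25 − D² × p(1 − p). At D = 1.0 this is 2.25 − 0.250 = 2.000, so the within-stratum SD is 1.414 and the adjusted SE is 1.414 × 0.1952 = 0.276. The unadjusted SE is about 6% larger. The 95% CI width falls from 2 × 1.977 × 0.293 = 1.16 to 2 × 1.977 × 0.276 = 1.09 points.

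**Step 3: size and power of both tests**, exact balance, 200,000 simulated trials per cell. Noncentral t gives the same adjusted powers:

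| D (points) | SE ratio, unadjusted/adjusted | 95% CI width, adjusted (unadjusted 1.16) | Type I error, unadjusted | Power, unadjusted | Power, adjusted |
|---|---|---|---|---|---|
| 0 | 1.000 | 1.16 | 5.0% | 92.4% | 92.4% |
| 0.5 | 1.014 | 1.14 | 4.7% | 92.7% | 93.1% |
| 1.0 | 1.062 | 1.09 | 3.7% | 93.5% | 94.9% |
| 1.5 | 1.157 | 1.00 | 2.3% | 95.1% | 97.5% |

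The adjusted type I error is 5.0% throughout. Unadjusted power also rises with D because total SD is held fixed while the true sampling error shrinks; it rises less than adjusted power. With equal strata, the share of variance explained is R² = (D²/4)/2.25. The precision gain then matches an unadjusted trial of 140/(1 − R²) patients: 140, 144, 158 and 187.

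**Step 4: loss after randomisation.** Section 8.2 states that "it is expected that up to 30% of patients will not be evaluable due to various reasons", so exact balance need not survive among the 140. Under random loss from 200 to 140 (100,000 trials):

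| D (points) | Type I error, unadjusted (50% / 64% liver) | Power, unadjusted vs adjusted, 50% liver | Same, 64% liver (assumed) |
|---|---|---|---|
| 0 | 5.0% / 5.0% | 92.3% vs 92.2% | 92.3% vs 92.2% |
| 0.5 | 4.7% / 4.9% | 92.4% vs 92.8% | 92.4% vs 92.9% |
| 1.0 | 4.0% / 4.3% | 93.0% vs 94.7% | 92.9% vs 94.5% |
| 1.5 | 3.1% / 3.2% | 93.9% vs 97.3% | 93.9% vs 97.0% |

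The test is less conservative than under exact balance, but the power gain is similar or slightly larger. A one-patient shift between strata moves unadjusted power to 92.6% or 94.3% at D = 1.0, and to 93.8% or 96.1% at D = 1.5, depending on direction. Adjusted power stays at 94.9% and 97.4–97.5%.

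**Step 5: rank test** (exact balance, normal data, 60,000 trials). Wilcoxon versus van Elteren power is 91.0% vs 90.8%, 91.4% vs 91.7%, 92.2% vs 93.8% and 93.5% vs 96.7% for D = 0, 0.5, 1.0 and 1.5. Wilcoxon type I error is 5.0%, 4.7%, 3.8% and 2.3%; van Elteren holds 5.0%.

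**Step 6: mixed model.** With complete data and a stratum effect constant over time, the treatment main effect is a contrast of patient means, so a similar gain applies. The treatment-by-time contrast is within patient and is unchanged.

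**The case against.** The strongest counter-argument is about weight. The benefit depends on a liver-pancreas difference the documents do not supply. At 0.5 points or less the power gain is 0.4 percentage points or less on a base above 92%. The visible gains need differences of 1.0 to 1.5 points; 1.0 equals the whole planned treatment effect and 1.5 is 25% of total variance. The planned test keeps its type I error at or below 5%, and the power statement is correct. All of this stands, and it makes the point an improvement rather than a correction.

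It is also fair that exact balance overstates the conservatism expected after 30% loss: at D = 1.5 the type I error is 3.1–3.2% under random loss, against 2.3%. That loss does not weaken the case for adjusting, since the power gain does not shrink.

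Adjustment is not strictly costless. With no stratum difference, van Elteren gives up about 0.2 percentage points to Wilcoxon, and the linear model at most about 0.1. Those costs are trivial. Finally, the mixed-model sentence uses the word including, so its list of terms may not be exhaustive. That leaves room in the mixed model but not in the primary test.

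The sample size calculation being based on a t-test is no obstacle: adjusted power is essentially the same without a stratum effect and higher with one.

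**Conclusion.** The concern holds. The plan randomises by resection type and then omits it from the primary pain test, the time-point tests and the listed mixed-model terms. The consequence is a possible loss of precision, with no inflation of false positives and no error in the 92% power.

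Over the assumed range, the unadjusted standard error is 0% to 16% too large. The power forgone is 0 to 2.4 percentage points under exact balance, and up to about 3 under random loss at the 1.5-point upper case. These figures assume a total SD of 1.5, roughly equal strata and normally distributed patient means. The gain is probably small, but the change costs almost nothing and should be made.

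**What to change.** In section 8.1:

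1. Make the primary analysis a linear model of the 48-hour time-averaged pain AUC on arm plus resection type as assigned at randomisation, reporting the adjusted mean difference with its 95% CI.
2. Add resection type to the pain mixed model.
3. If a rank test is used, make it the van Elteren (stratified Wilcoxon) test.
4. Keep the unadjusted t-test as a sensitivity analysis.

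Separately, state how a combined resection is assigned to a stratum at randomisation. Section 3.1 admits "Patients undergoing liver and/or pancreatic surgical resection for malignancy", while the factor has only two levels. This is a point of definition and adds no weight to the finding.

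The cost is two or three sentences for the analysis itself. No new data or patients are needed, and the power statement in section 8.2 can stay.
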